## 13 Publication of research findings

Publication of the results of this trial will be governed by the policies and procedures developed by the Steering and Dissemination Committees.

## 15 Appendix 1: Chronic LBP Questionnaire

| Screening for Chronic Low Back Pain |  |
|-------------------------------------|--|
| 1.                                  | How long has low back pain interfered with your ability to do regular daily activities?

 Less than 1 month
 1 – 3 months
 More than 3 months                                 |
| 2.                                  | Think only about the past 6 months . How often has low back pain interfered with your ability to do regular daily activities?

 Less than half the days
 Half the days or more than half the days |

### Definition and questionnaire rules:

- “Chronic” = greater than 3 months (Q1c) + at least half the days (Q2b)
- “Acute” = all else Q1a, Q1b, or Q1c+Q2a
- If patient answers 1a or 1b, stop and patient is acute
- If patient answers 1c, proceed to question 2
- If patient answers 2a, patient is acute
- If patient answers 2b, patient is chronic

## 16 Appendix 2: STarT Back Tool

| STarT Back Screening Tool for Risk Stratification  |   |                          |                          |                          |
|--|---|--------------------------|--------------------------|--------------------------|
| Thinking about the last 2 weeks , check your response to the following questions: |   |                          |                          |                          |
|  |   |                          | Disagree                 | Agree                    |
|  |   |                          | 0                        | 1                        |
| 1.   | My back pain has spread down my leg(s) at some time in the last 2 weeks            |  |  |                          |
| 2.   | I have had pain in the shoulder or neck at some time in the last 2 weeks    |  |  |                          |
| 3.   | I have only walked short distances because of my back pain                         |  |  |                          |
| 4.   | In the last 2 weeks, I have dressed more slowly than usual because of my back pain |  |  |                          |
| 5.   | It's not really safe for a person with a condition like mine to be physically active      |  |  |                          |
| 6.   | Worrying thoughts have been going through my mind a lot of the time                |  |  |                          |
| 7.   | I feel that my back pain is terrible and it's never going to get any better |  |  |                          |
| 8.   | In general I have not enjoyed all the things I used to enjoy                       |  |  |                          |
| 9.   | Overall, how bothersome has your back pain been in the last 2 weeks ?       |                          |                          |                          |
|  | Not at all  | Slightly                 | Moderately               | Very much                |
|  |   |  |  |  |
|  | 0   | 0                        | 0                        | 1                        |
| Total Score (all 9):   |   | Sub Score (Q5–9):        |                          |                          |
| Scoring System  |   |                          |                          |                          |
| Low Risk:  | Total Score = 3 or less   |                          |                          |                          |
| Medium Risk:   | Total Score = 4 or more + Sub Score Q5–9 = 3 or less                                      |                          |                          |                          |
| High Risk:   | Total Score = 4 or more + Sub Score Q5–9 = 4 or more                                      |                          |                          |                          |

## 17 Appendix 3: Oswestry LBP Questionnaire

| Oswestry LBP Questionnaire  |   |
|--|---|
| 
This questionnaire is designed to give us information as to how your back (or leg) trouble affects your ability to manage in everyday life. Please answer every section. Mark one box only in each section that most closely describes you today.
   |   |
| 
Section 1 – Pain Intensity
 
 I have no pain at the moment.
 
 The pain is very mild at the moment.
 
 The pain is moderate at the moment.
 
 The pain is fairly severe at the moment.
 
 The pain is very severe at the moment.
 
 The pain is the worst imaginable at the moment.
 
Section 2 – Personal Care (washing, dressing, etc.)
 
 I can look after myself normally without causing additional pain.
 
 I can look after myself normally but it is very painful.
 
 It is painful to look after myself and I am slow and careful.
 
 I need some help but manage most of my personal care.
 
 I need help every day in most aspects of self care.
 
 I do not get dressed, I wash with difficulty and stay in bed.
 
Section 3 – Lifting
 
 I can lift heavy weights without additional pain.
 
 I can lift heavy weights but it gives additional pain.
 
 Pain prevents me from lifting heavy weights off the floor but I can manage if they are conveniently positioned, e.g. on a table.
 
 Pain prevents me from lifting heavy weights but I can manage light to medium weights if they are conveniently positioned.
 
 I can only lift very light weights.
 
 I cannot lift or carry anything at all.
 
Section 4 – Walking
 
 Pain does not prevent me from walking any distance.
 
 Pain prevents me from walking more than one mile.
 
 Pain prevents me from walking more than a quarter of a mile.
 
 Pain prevents me from walking more than 100 yards.
 
 I can only walk using a cane or crutches.
 
 I am in bed most of the time and have to crawl to the toilet.
 
Section 5 – Sitting
 
 I can sit in any chair as long as I like.
 
 I can sit in my favorite chair as long as I like.
 
 Pain prevents me from sitting for more than 1 hour.
 
 Pain prevents me from sitting for more than half an hour.
 
 Pain prevents me from sitting for more than 10 minutes.
 
 Pain prevents me from sitting at all.
 | 
Section 6 – Standing
 
 I can stand as long as I want without additional pain.
 
 I can stand as long as I want but it gives me additional pain.
 
 Pain prevents me from standing for more than 1 hour.
 
 Pain prevents me from standing for more than half an hour.
 
 Pain prevents me from standing for more than 10 minutes.
 
 Pain prevents me from standing at all.
 
Section 7 – Sleeping
 
 My sleep is never interrupted by pain.
 
 My sleep is occasionally interrupted by pain.
 
 Because of pain I have less than 6 hours sleep.
 
 Because of pain I have less than 4 hours sleep.
 
 Because of pain I have less than 2 hours sleep.
 
 Pain prevents me from sleeping at all.
 
Section 8 – Sex Life (if applicable)
 
 My sex life is normal and causes no additional pain.
 
 My sex life is normal but causes some additional pain.
 
 My sex life is nearly normal but is very painful.
 
 My sex life is severely restricted by pain.
 
 My sex life is nearly non-existent because of pain.
 
 Pain prevents me from having any sex life at all.
 
Section 9 – Social Life
 
 My social life is normal and causes me no additional pain.
 
 My social life is normal but increases the degree of pain.
 
 Pain has no significant effect on my social life apart from limiting my more energetic interests, e.g., sport, etc.
 
 Pain has restricted my social life and I do not go out as often.
 
 Pain has restricted my social life to home.
 
 I have no social life because of pain.
 
Section 10 – Traveling
 
 I can travel anywhere without pain.
 
 I can travel anywhere but it gives me additional pain.
 
 Pain is bad but I am able to manage trips over two hours.
 
 Pain restricts me to trips of less than one hour.
 
 Pain restricts me to short necessary trips of under 30 minutes.
 
 Pain prevents me from traveling except to receive treatment.
 |
| 
ODI © Jeremy Fairbank 1980. All Rights Reserved. Version 2.1a
   |   |

## 18 Appendix 4: Physical Therapist Checklist

Thank you for this referral to *(Insert Clinic Name)* . The following is a summary of content areas covered (indicated by checked boxes) with this patient during treatment for their acute low back pain, based on your initial referral of / / .

### Patient Information:

Patient Name: \_\_\_\_\_ HICN: \_\_\_\_\_ DOB: / /  
Diagnosis Indicating Therapy: \_\_\_\_\_ ICD-10 Code: \_\_\_\_\_  
Referring Physician: \_\_\_\_\_ Start of Care Date: / /

### Progress Content Areas:

[figure not shown]
- **Communication**
  - Active listening (eye contact, paraphrase/repeat back what patient says)
  - Facilitation of self-disclosure, activation philosophy (elicit patient's concerns, discuss and reassure RE: activity)
  - Patient centered goal-setting / motivational interviewing (connect with patient RE: shared goals)
- **Pain coping skills taught and reinforced**
  - Relaxed breathing
  - Adaptive distraction skills (e.g., pleasant place imagery)
  - Balanced statements to counteract unhelpful thinking styles (e.g., pain catastrophizing, all-or-nothing thinking)
- **Activity-based treatment**
  - Graded activity (to reduce pain-related activity avoidance)
  - Graded exposure (to reduce fear-related motion avoidance)
- **Physical impairment component – most appropriate classification (from APTA clinical practice guidelines):**
  - Acute/subacute LBP with mobility deficits
  - Acute/subacute LBP with movement coordination impairments
  - Acute LBP with related (referred) lower extremity pain
  - Acute/subacute LBP with radiating pain
- **Home exercise program:**
  - Specific activities integrating pain coping skills (as described above)
  - Specific education (e.g., web-based format)
- **Treatment monitoring completed:** Yes  No

### Additional comments:

Therapist's Name: \_\_\_\_\_ Date: / /

*(Completed checklist is to be forwarded to office of referring PCP via electronic scan or fax.)*

## 19 Appendix 5: Flow diagram for each regional site

## 20 Appendix 6: Data from electronic medical record

### Contact information (for 6- and 12-month assessments)

- Name
- Street address
- Electronic mail address
- Telephone number

### Baseline sociodemographic variables

- Sex
- Race
- Hispanic ethnicity
- Date of birth
- Height
- Weight
- Body mass index
- Tobacco use
- Comorbid conditions
- Insurance status

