### 3.4 Study population and sites

The target population for this study will be adult patients who present to primary care physicians (i.e., internal medicine, family practice, and geriatric medicine physicians) with a primary complaint of LBP. Patients will be recruited from health systems in five regional areas that surround: 1) Pittsburgh, PA (UPMC); 2) Boston, MA (Boston Medical Center); 3) Baltimore, MD (Johns Hopkins Medicine); 4) Charleston, SC (Medical University of South Carolina); and 5) Salt Lake City, UT (Intermountain Healthcare). Within the individual regional areas, primary care clinics have been identified that represent community-based PCP clinics. In all instances, there are more potential sites than are required for successful completion of the trial, which will allow flexibility in the randomization scheme and alternatives should there be individual PCP-clinic recruitment shortfalls. This large, nation-wide group of clinics across five different health systems provides a high level of pragmatism for the PRECIS-2 organizational domain because the systems will be variable with regards to provider expertise, resources, and organizational structure.

Certain patient subgroups are of particular interest (**SA5**) given greater risk for poorer LBP outcomes as demonstrated in observational cohort studies. Adequate enrollment will be assured to have statistical power to conduct subgroup analyses of patients with lower socioeconomic status (using insurance as a proxy) and the comorbid conditions of smoking, depression, and obesity. Identification of subgroups will be based on information obtainable in the EMR. The participating primary care clinics will be sampled to reflect gender, race, and ethnicity proportions of the population being served at the recruitment sites.

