## 4 Selection and enrollment of participants

### 4.1 Inclusion criteria

Inclusion criteria for the study are:

- 1) 18 years of age or older, and
- 2) Receiving care for acute low back pain (i.e., does not meet the criteria for chronic LBP) during a primary care clinic visit.

An even distribution of age from 20-60 years of age is expected with a slight drop off after age 60, due to LBP becoming more of a chronic problem with aging. The lower age limit on recruitment of 18 years was included based on stakeholder feedback from internal medicine and family medicine colleagues that pointed out the different nature of LBP in adolescents. Gender is expected to be 50% male and race/ethnicity will closely match those in the geographical location of the sites. English language proficiency will not be an inclusion criterion because it is assumed that clinics with a significant non-English population will have translation capabilities for that population.

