## 9.5 Data analyses

- 9.5.1 **Primary outcome 1:** This initial analysis (**PA1**) will use a generalized linear mixed model with a logit link controlling for block set (see Randomization) and a fixed effect for intervention accounting for the cluster RCT design with a random clinic effect. Primary analyses will also adjust for patient characteristics (maladaptive pain coping behaviors such as catastrophizing and fear avoidance, functional impairment as measured by the Oswestry, and presence

of psychiatric comorbidities), as these have been associated with higher transition to chronic LBP. The intraclass correlation coefficients will also be estimated and reported for all outcome measures to assess the assumptions for sample size analyses and also for future investigations using similar designs and outcomes. Analysis for the secondary aims (**SA4** and **SA5**) will be largely descriptive assessing the proportion of patients who transition to chronic LBP among the low and moderate risk observational cohort. The proportion and confidence interval will be estimated using generalized linear models adjusting for clustering.

- 9.5.2 **Primary outcome 2:** This aim (**PA1**) will be analyzed using contrasts from a linear mixed models analysis for 6-month back-related function (Oswestry) controlling for baseline Oswestry and the block set (see Randomization). The intervention will first be explored by time interaction, and then proceed to a main effects model with only group and time. For the secondary aims (**SA4** and **SA5**) patient-centered outcomes, such as functional status, would use general linear models if deemed appropriate based on normality assumptions. If normality is hugely violated, a cutpoint for 'response' will be applied.

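### The primary model for transition to chronic LBP leaves out patient age and insurance status, both already extracted, so the primary estimate is not adjusted for patient-level imbalance or non-response linked to them

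*Combined protocol and SAP*

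**What the plan says.** Section 9.5.1 analyses PA1 with a "generalized linear mixed model with a logit link controlling for block set", a fixed intervention effect and a random clinic effect. The patient-level covariates are "maladaptive pain coping behaviors such as catastrophizing and fear avoidance, functional impairment as measured by the Oswestry", and the presence "of psychiatric comorbidities), as these have been associated with higher transition to chronic LBP". No other patient characteristic is listed.

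Other sections bear on that list:

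- **Appendix 6** puts date of birth, "Insurance status", tobacco use and "Body mass index" among the baseline variables taken from the medical record.
- **Section 3.4** singles out lower socioeconomic status (insurance as proxy), smoking, depression and obesity as subgroups of interest "given greater risk for poorer LBP outcomes as demonstrated in observational cohort studies".
- **Section 4.1** expects fewer patients above age 60 "due to LBP becoming more of a chronic problem with aging".
- **Sections 1.2.5 and 9.1.13** describe the link of smoking and obesity with transition as uncertain or unclear.
- **Section 9.1.15** names age, gender and health insurance as characteristics for comparing patients with and without complete data, by treatment group. **Section 9.2.2** allows for 40% non-response.
- **Section 9.2.5** compares clinic and patient characteristics between arms and adjusts for differences in sensitivity analyses.
- **Section 3.2** orders clinics by back pain volume to form blocks, then orders them within block by percentage Medicaid or self-pay before allocation.

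**The concern.** The plan justifies its covariates by their association with transition, and section 3.4 attaches poorer outcomes to lower socioeconomic status. Yet of the four factors in section 3.4, only depression has a counterpart in the primary model, through psychiatric comorbidity. No reason is given for leaving insurance out.

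This matters in two ways. First, clinics are allocated before patients are identified, and only intervention clinics are coached on referral. The patients enrolled can therefore differ between arms by chance or by recruitment, and clinic randomization does not control the latter. Second, the primary outcome is observed only in responders. If response depends on age or insurance, a model that conditions on both remains valid for that kind of missingness. A model that omits them does not in general.

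**Working it through.** **1. The plan's own power.** Section 9.2.3 gives 30 clinics per arm, 10 to 14 completers per clinic, ICC 0.05, a control rate of 25% to 30% and a 40% relative reduction. Two-sided alpha 0.05 is stated only for Table 3 and is assumed here.

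- Effective n per arm = 30n / (1 + (n − 1) × 0.05).
- n = 14, control 25%: 420 / 1.65 = 254.5, power 80.7%.
- n = 10, control 30%: 300 / 1.45 = 206.9, power 81.8%.

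The stated figure of just over 80% reproduces at these two pairings, with no covariate gain in it. Other pairings give 72.2% (n = 10, 25%) to 88.9% (n = 14, 30%).

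**2. Target and sample.** At the mid control rate of 27.5%, a 40% reduction gives 16.5%, a difference of 11 points and an average rate of 22%. Completers: 1,860 × 0.6 = 1,116, or 558 per arm and 18.6 per clinic. Expected events: 1,116 × 0.22 ≈ 246.

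**3. Chance imbalance per factor.** Prevalences are borrowed from Table 3: underserved 665/2,464 = 27%, obese 640/2,464 = 26%, smokers 493/2,464 = 20%. That table describes the low- and medium-risk cohort, so their use for high-risk patients is an assumption. The ICC of each characteristic is assumed to be 0.02 to 0.10. The cluster-size coefficient of variation, 0.65, is from section 9.2.2.

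- Design effect = 1 + ((1 + 0.65²) × 18.6 − 1) × ICC = 1.51 at 0.02 and 3.55 at 0.10.
- SD of the arm difference = √(2q(1 − q)/558 × design effect).
- For insurance, q = 0.27: 3.3 to 5.0 points, so a 95% range of ±6.4 to 9.8 points. Across the three factors the range is ±5.8 to 9.8 points.

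The formula ignores stratification, so the insurance figure is too wide to the extent that section 3.2 balances clinic mix.

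**4. Effect on the arm contrast.** The documents give no prognostic strength for high-risk patients. Relative risks (RR) of 1.3 to 1.4 are assumed.

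- Risk difference between patients with and without a factor = 0.22 × (RR − 1) / (1 + q(RR − 1)).
- For insurance: 0.22 × 0.3 / 1.081 = 6.1 points, to 0.22 × 0.4 / 1.108 = 7.9 points.
- Insurance alone, 95% range of the shift: 1.96 × 0.061 × 3.3 ≈ 0.4 points, to 1.96 × 0.079 × 5.0 ≈ 0.8 points.
- Insurance, smoking and obesity combined, with imbalances correlated 0 to 0.3 (assumed): about ±0.7 to 1.7 points, or 6% to 15% of the 11-point target.

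Age is not included, because the documents give nothing to size its effect.

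**5. Precision.** The share of outcome variance explained is q(1 − q) × (risk difference)² / (0.22 × 0.78), summed over the three factors. This is about 0.012 at RR 1.3 and 0.021 at RR 1.4. Dividing the effective n by (1 − R²) takes the 80.7% in step 1 to 81.1% at R² = 0.01 and 81.5% at R² = 0.02. A simulation on the logit scale (600 runs, 12 completers per clinic, 25% control rate, three binary covariates and one continuous covariate, fitted by GEE) changed power by 0.0 points at an odds ratio of 1.3, +0.3 at 1.5 and +1.5 at 2.0. Neither calculation includes the covariates already planned, which would absorb part of the gain.

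**The case against.** The strongest reply is that the plan has a reasoned, prespecified covariate set, and that a longer one is a preference. It also has other safeguards: sensitivity analyses for observed differences (9.2.5), allocation that orders clinics by insurance mix (3.2), block set in the model, and multiple imputation (9.1.15). Averaged over randomizations, chance imbalance does not bias the comparison.

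Much of this stands, and it rules out several stronger readings.

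- **That protection is wholly given up.** It is not. But the sensitivity covariates are chosen after the data are seen, and no rule says which result prevails if they disagree. Blocks are formed on volume, and Medicaid share is a clinic figure, not the status of enrolled responders. Imputation is a sensitivity analysis whose variables are not listed.
- **That the omission inflates the false-positive rate.** A simulation gave 8% to 10%, but only given an 8-point difference in insurance, smoking and obesity all adverse to one arm. The chance of that, in either direction, is about 0.0000003 to 0.0002 if the imbalances are independent, and 0.0003 to 0.009 if they are correlated 0.5 (assumed). It is not the trial's error rate.
- **That Table 3 shows 25% to 40% higher risk in these subgroups.** Those are detectable differences in a power table for another cohort.
- **That smoking and obesity belong in the model on the same footing.** Sections 1.2.5 and 9.1.13 call their link with transition uncertain or unclear.
- **That section 4.1 makes age a predictor of transition.** It explains the expected age distribution. The firmer reason for age is section 9.1.15.
- **That precision is materially lost.** In a logit model, adjustment does not shrink the standard error of the log odds ratio. Any gain comes through the conditional effect and is slight.

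**Conclusion.** The point holds for age and insurance, as a minor improvement. The primary PA1 estimate is unadjusted for patient-level differences in two variables that the plan already collects and itself regards as relevant to missingness, one of which it also links to poorer outcomes.

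The size is modest: about ±0.7 to 1.7 points for three factors together and ±0.4 to 0.8 for insurance alone, before any credit for stratification. These figures rest on assumed relative risks, assumed ICCs of the characteristics, and prevalences from the lower-risk cohort. They cover chance only. Shifts from differential recruitment or non-response could be larger or smaller, and the documents give no figures to size them. The case for the change is protection of the primary estimate at almost no cost, not power.

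**What to change.** In section 9.5.1, add two fixed effects to the PA1 model, both taken at the index visit: patient age (continuous) and insurance (Medicaid or none versus other). Tobacco use and body mass index may be added if the team wishes, with a note that section 1.2.5 treats their influence as uncertain.

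State that blank record fields get a missing category or simple imputation, so that no patient drops out of the primary analysis. Keep the section 9.2.5 sensitivity analyses for any other imbalance.

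The cost is a change of wording and two to four extra parameters (plus any missing category) against roughly 250 expected events. No new data are needed. Section 6.2.3 sets no site limit on the baseline extract; confirm that it covers all five regions, since the 12-month resource-use extract covers only four.
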